 - Inability to taper steroids to 10 mg or less prednisone or equivalent within 12 weeks
 - SAEs/AEs of Grade ≥ 2 deemed intolerable by the patient or the treating physician and not responding to medical management and any SAEs/AEs of \geq Grade 3 that do not recover to Grade 1 or less within 12 weeks
 - Persistent Grade 2-3 AEs that do not recover to Grade 1 or less within 12 weeks
 - Grade 3 to 4 AEs that are classified as immune-related by the Investigator but are not listed in Appendix 10.1 if they do not resolve to Grade ≤ 1 or baseline with immunosuppressive therapy within 2 weeks.

- \geq Grade 4 drug-related AEs.

Given the patient's agreement, the patient will undergo the procedures for early treatment discontinuation and will be followed up as outlined in [Part A Flow Chart](#), [Part B Flow Chart](#), [Part C Lung Flow Chart](#), and Section 6.2.3.1. For all patients the reason for withdrawal from trial treatment (e.g., adverse events) must be recorded in the CRF. These data will be included in the trial database and reported.

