5.2.6.4.1 Dose-limiting toxicities

DLTs are considered to be AESIs, and must be reported as such. The definition of DLTs is presented in Section 0.

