5.2.6.4.4 Immune-related adverse events (irAE)

Immune-related AEs are AEs associated with immunotherapy treatments that appear to be associated with the immune therapy's mechanism of action. These adverse reactions, which can be severe, may involve the gastrointestinal, skin, liver, endocrine, respiratory, renal, or other organ systems. The Sponsor has defined a list of potential irAEs in [Table 10.1: 1](#) in [Appendix 10.1](#). These irAEs must be reported as AESIs. If an Investigator determines another event (not on the list) should be a potential irAE, the Investigator may also report that event as an AESI. Immune-related AEs should be reported as AESIs only for patients who received immunotherapy.

Recommendations for the management of irAEs are presented in [Appendix 10.2](#).

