
Ocular (report as an irAE if \geq Grade 2 or any grade resulting in dose modification or use of systemic steroids to treat the AE)
 
 • Uveitis • Iritis

Table 10.1: 1 Immune-related adverse events of special interest (continued)

Renal (reported as an irAE if ≥ Grade 2)

 • Nephritis • Nephritis autoimmune • Renal failure • Renal failure acute • Creatinine elevations (report as an irAE if ≥Grade 3 or any grade resulting in dose modification or use of systemic steroids to treat the AE)
Skin (reported as an irAE for any grade)

 • Dermatitis exfoliative • Erythema multiforme • Stevens-Johnson syndrome • Toxic epidermal necrolysis
Skin (reported as an irAE if ≥ Grade 3)

 • Pruritus • Rash • Rash generalized • Rash maculopapular • Any rash considered clinically significant in the physician's judgment
Other (reported as an irAE for any grade)

 • Myocarditis • Pancreatitis • Pericarditis • Any other Grade 3 event that is considered immune-related by the physician

*Immune-related AEs should be reported as AESIs only for patients who received immunotherapy.

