In case of prolonged steroid therapy or treatment with immunosuppressives consider the possibility of opportunistic infections and tuberculosis reactivation. Careful monitoring and consideration of administration of prophylactic antibiotics where appropriate are warranted.

Commonly, referral to experts in the management of organ-specific conditions is highly recommended, especially for irAEs grade 3 or grade 4, or irAEs where management is complex.

BI 754091 and BI 891065 should be permanently discontinued for immune related

- encephalitis, aseptic meningitis, transverse myelitis, or Guillain-Barre syndrome of any grade
- acquired thrombotic thrombocytopenic purpura of any grade
- myocarditis of any grade
- myasthenia gravis, peripheral neuropathy or autonomic neuropathy of grade ≥ 3
- myositis grade 2 with objective findings (see below), any myositis grade ≥ 3
- hepatitis grade ≥ 3 (transaminase >5 times ULN or total bilirubin >3 times ULN), recurrent hepatitis grade ≥ 2
- nephritis grade ≥ 3 , persisting grade 2 nephritis unresponsive to initial steroid therapy or worsening, and recurrent nephritis grade ≥ 2
- pneumonitis grade ≥ 3
- rash, bullous dermatoses, severe cutaneous adverse reaction, Stevens Johnson Syndrome, toxic epidermal necrolysis of grade 4, and recurrent rash grade ≥ 3
- colitis grade 4, and recurrent colitis of any grade
- uveitis, iritis, episcleritis of grade ≥ 3
- autoimmune-hemolytic anemia grade ≥ 2
- haemolytic uremic syndrome grade ≥ 3
- immune thrombocytopenia grade 4

- any recurrent irAE grade ≥ 3 ,
- inability to taper steroids to 10 mg or less prednisone or equivalent within 12 weeks, or
- persistent Grade 2-3 AEs that do not recover to Grade 1 or less within 12 weeks.

Dose adjustment of BI 754091 and BI 891065 besides interrupting or permanently discontinuing BI 754091 and BI 891065 are not allowed.

In rare situations when benefit and risk assessment is considered positive for a patient to continue BI 754091 and BI 891065 treatment despite guidance to permanently discontinue (e.g. in case no alternative anti-cancer therapy is available), it should be discussed with the sponsor.

Pneumonitis:

- For Grade 1 pneumonitis with radiographic evidence of worsening, withhold BI 754091 and BI 891065 until improvement or resolution; BI 754091 and BI 891065 may be reintroduced upon radiographic improvement. In the absence of radiographic improvement within 3-4 weeks, follow guidance as for grade 2 event.

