7.8.1 Adverse events

The analyses of AEs will be descriptive in nature. All analyses will be based on the number of patients with AEs (not on the number of AEs). The analysis will be based on BI standards (6). AEs will be coded using the most recent version of MedDRA. According to the BI standards multiple overlapping or adjacent recordings (AE occurrences) of the same AE are collapsed into one AE event if all AE attributes are identical (lower level term, severity, action taken, therapy required, seriousness, reason for seriousness, relationship, outcome, AE of special interest (AESI) flag).

The analyses of AEs will be based on the concept of treatment-emergent AEs, where a treatment-emergent AE has an onset in the analysing treatment period. The AE analysis will be based on the on-treatment period which starts with the date of the first administration of study medication and ends 30 days after the last administration of study medication. AEs with an onset date in the screening period (time between informed consent date and date of the first administration of study medication) or follow-up period (time after the on-treatment period) will be tabulated and listed separately.

Sorting order: In AE tables, system organ classes (SOCs) will be sorted alphabetically and preferred terms (PTs, within SOCs) will be sorted by descending frequency.

Listings of AEs will be displayed by patient. The actual planned dose of BI 891065/dose combination of BI 891065 and BI 754091 will be derived and included in the listings. AEs will be reported with start day and end day as calculated from the first day of treatment with study medication. For listings displaying AEs during the screening or follow-up period, the start and stop day are calculated from the start of the respective analysis period.

The incidence of AEs overall, related AEs, serious AEs (SAEs), and immune-related AEs will be reported by severity according to common terminology criteria for adverse events (CTCAE) grades (CTCAE version 4.03 for Part A, CTCAE version 5.0 for Part B and Part C). Drug-related serious AEs will also be tabulated. Protocol-specified AESI will be analysed based on data reported in the eCRF.

AEs leading to death during the on-treatment period will be tabulated by SOC and PT. Reported fatal AEs during the follow-up period will be listed.

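### The catch-all row of the immune-related AESI table stops at Grade 3 and several Appendix 10.2 conditions have no row, so in Part B some immune-related events lack mandatory labelling, rapid reporting or late collection

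*Protocol*

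**What the plan says.** Protocol Section 5.2.6.4.4 points to the sponsor's list in Table 10.1: 1 and says of the listed events "These irAEs must be reported as AESIs". For an event off the list that the investigator thinks is immune-related, "the Investigator may also report that event as an AESI". Both apply only to patients who received immunotherapy.

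The last group of the table is headed "Other (reported as an irAE for any grade". It names myocarditis, pancreatitis and pericarditis, and ends with the catch-all row: "Any other Grade 3 event that is considered immune-related by the physician".

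Appendix 10.2 calls for permanent discontinuation for "encephalitis, aseptic meningitis, transverse myelitis, or Guillain-Barre syndrome of any grade", and gives grade-by-grade guidance for many other conditions. Section 3.3.4.1 has a withdrawal rule for "Grade 3 to 4 AEs that are classified as immune-related by the Investigator but are not listed in Appendix 10.1", applied when the event does not resolve within 2 weeks on immunosuppressive therapy.

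There is a second mandatory route. Section 5.2.6.4.1 says "DLTs are considered to be AESIs, and must be reported as such".

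SAP Section 7.8.1 reports the incidence of immune-related AEs by CTCAE grade. In a separate sentence it adds: "Protocol-specified AESI will be analysed based on data reported in the eCRF".

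**The concern.** Read literally, an immune-related event that the table does not name is a mandatory irAE AESI at Grade 3 and optional at Grade 4, which is the wrong way round for a safety list. Some conditions serious enough to end treatment at any grade are not named at all.

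AESI status has practical consequences. It triggers 24-hour reporting (Section 5.2.6.7.2), and after the residual effect period it decides whether a related non-serious event is collected (Section 5.2.6.7.1). Immune-related toxicity is a central safety question once BI 754091 is added in Part B.

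**Working it through.** The plan gives no figure to reproduce here, so the check is a comparison of passages.

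**1. The catch-all row.** The group thresholds in Table 10.1: 1 are written as a grade or higher; this row is not. It also conflicts with its own heading, since a row restricted to Grade 3 cannot apply at any grade. It does not fit Section 3.3.4.1 either: if every Grade 3 event judged immune-related is already listed by this row, none can be unlisted, yet the withdrawal rule speaks of unlisted events of Grade 3 to 4.

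**2. Conditions in Appendix 10.2 without a row.**
- Permanent discontinuation at any grade: encephalitis, aseptic meningitis, transverse myelitis. Guillain-Barré syndrome, in the same sentence of Appendix 10.2, does have a row.
- Managed by grade: myositis, inflammatory arthritis, polymyalgia-like syndrome.

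That makes six. Bullous dermatosis and episcleritis are not named either, but they lie close to existing skin and ocular rows, so I leave them out of the count.

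**3. What is mandatory for an unlisted event judged immune-related.** The DLT criteria come from Section 4.1.8, where DLTs are recorded throughout the trial.

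| Event | Catch-all row | DLT rule | Result |
|---|---|---|---|
| Grade 3 | Applies | Usually applies; resolving Grade 3 irAEs are exempt | Mandatory AESI, labelled irAE |
| Grade 4 non-haematologic | Does not apply as written | Applies; the irAE exemption covers only Grade 3 | Mandatory AESI as a DLT; irAE label optional |
| Grade 4 amylase or lipase rise without pancreatitis | Does not apply | Expressly exempt | Not a mandatory AESI |
| Grade 4 neutropenia of 5 days or less, without fever or infection | Does not apply | Criterion not met | Not a mandatory AESI |
| Grade 1-2 | Does not apply | Narrow cases only, e.g. persistent related Grade 2 toxicity that prevents BI 754091 on Cycle 2 Day 1 | Usually not a mandatory AESI |

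An event that meets a seriousness criterion is in any case an SAE, with the same 24-hour deadline.

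**4. Collection over time (Section 5.2.6.7.1).** Until the end of the 30-day residual effect period all AEs are collected, whatever their label. After that, only related SAEs and related AESIs are. A related, non-serious Grade 2 myositis or arthritis that starts later therefore need not be recorded unless the investigator chooses to call it an AESI.

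**5. The SAP.** Section 7.8.1 names immune-related AEs and protocol-specified AESIs in different sentences, and only the second is tied to eCRF data. The available text does not say whether an AE is classed as immune-related by the table, by the AESI flag or by investigator attribution. Events that start after the residual effect period are shown separately from the on-treatment tables, so the gap in step 4 affects the follow-up display, not on-treatment incidence.

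**6. Scope and scale.** Part A is monotherapy with BI 891065, and irAE AESIs apply only after immunotherapy. Part C enrolled nobody (SAP Section 4). That leaves Part B, planned at 31-37 patients. One patient is 1/37 = 2.7% to 1/31 = 3.2% of that group. This is the weight of any single patient, not an estimate of how many events are missed.

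**The case against.** The strongest objection is the DLT route. All six missing conditions are non-haematologic, so at Grade 4 each is a mandatory AESI through Section 5.2.6.4.1. This stands, and it removes most of the Grade 4 problem. What it leaves is the irAE label and the two exceptions in the table above.

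A reader might infer that Grade 4 or low-grade irAEs are under-counted in the SAP's irAE table. The documents do not show this. No visible SAP text says that table is drawn from Table 10.1: 1, and the selection rule may sit in technical documents or in the sponsor's AE standard. Section 3.3.4.1 itself recognises immune-related events that are not listed. Events up to the end of the residual effect period stay in the overall AE tables by grade, and those leading to permanent discontinuation are also tabulated as other significant AEs.

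A reader might also infer an effect on the MTD, because late immune-related DLTs are defined in terms of irAEs. That does not follow. The definition in Section 4.1.8 does not refer to the table, the end-of-escalation rerun uses all DLTs, and SAP Section 7.4 counts DLTs over the whole on-treatment period.

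Finally, an expedited-reporting list need not match a management appendix. That is fair as a general principle, and the low-grade omissions could be deliberate. It does not explain a row that takes in Grade 3 but not Grade 4, the clash with the heading, or the mismatch with Section 3.3.4.1.

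**Conclusion.** The defect in the table is real and its consequence is modest. In Part B it comes to three things:

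- Grade 4 unlisted events are not required to carry the irAE label.
- A few Grade 4 events outside the DLT rule are not mandatory AESIs.
- Grade 1-2 unlisted irAEs need no 24-hour report and, if non-serious and starting after the 30-day residual effect period, need not be collected.

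Under-counting in the SAP irAE table is possible, not established, and there is no effect on the MTD model. The documents give no rate for such events, so the scale is limited to 2.7 to 3.2 percentage points for each patient affected.

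This rests on a literal reading of the Grade 3 row. It also assumes that the events are not serious on other grounds; the list of always-serious events is kept outside these documents, so I cannot tell which of the six conditions it covers.

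**What to change.** - **Table 10.1: 1, catch-all row:** change Grade 3 to Grade 3 or higher, and resolve the conflict with the heading, for example by moving the row to its own group.
- **Table 10.1: 1, missing conditions:** add reporting rows for the six conditions, at any grade where Appendix 10.2 acts at any grade.
- **SAP Section 7.8.1:** state that the irAE table includes listed events plus any event the investigator classifies as immune-related. Using the list alone would exclude unlisted low-grade events.
- **Section 3.3.4.1:** reconcile it with Section 5.2.6.4.4, Table 10.1: 1 and Appendix 10.2 in the same amendment. Its withdrawal rule depends on what Appendix 10.1 does not list. Once the row covers Grade 3 or higher, no Grade 3 or 4 event judged immune-related would be unlisted, and the rule would have nothing to apply to. The sponsor should decide what that rule is meant to cover, so that a reporting edit does not change a treatment rule by accident.

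The cost is a few table rows, a SAP sentence, a cross-check of four places and a few more AESI forms.

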10.2 MANAGEMENT OF IMMUNE-RELATED ADVERSE EVENTS

Regarding diagnosis, grading and therapeutic management of immune-related adverse events, grading and treatment, up-to-date published guidelines should be considered (e.g. P19-00269). Only limited guidance on management of specific irAEs can be given here.

Please refer to published guidelines (e.g. ASCO guideline, Brahmer [P19-00269]) for details.

In general,

- BI 754091 and BI 891065 should be continued with close monitoring in case of grade 1 irAEs, with the exception of irAEs that may rapidly evolve into severe or fatal conditions (encephalitis of any grade, myocarditis of any grade, pneumonitis that is grade 1 but shows radiographic evidence of worsening – see detailed guidance below).
- For most Grade 2 irAEs, BI 754091 and BI 891065 should be withheld and treatment with corticosteroids is commonly warranted, usually with an initial dose of 0.5 to 1 mg/kg prednisone / prednisone equivalent daily. Restart of therapy is commonly possible once symptoms and/or laboratory values have resolved to grade 1 or less, and on ≤ 10 mg prednisone / prednisone equivalent per day.
- For Grade 3 irAEs, BI 754091 and BI 891065 has to be withheld, and treatment with high-dose corticosteroids (1-2mg/kg/d prednisone / prednisone equivalent) is usually warranted. Upon improvement, steroids should be tapered slowly over 4-6 weeks. Non-steroidal immunosuppressives (e.g. infliximab, mycophonlate mofetil) should be considered if no improvement or worsening occurs within the initial 48 to 72 hours. Upon recovery to grade 1 or less, and on ≤ 10 mg prednisone / prednisone equivalent per day, restarting BI 754091 and BI 891065 may be considered for selected irAEs, but caution is advised, in particular in patients with early-onset irAEs. Expert consultancy and agreement with medical monitor is recommended prior to restart of therapy.
- Most Grade 4 irAEs warrant permanent discontinuation of BI 754091 and BI 891065.
- Restart of therapy is commonly possible for endocrine irAEs regardless of grade once stable hormone replacement has been instituted and symptoms have recovered. In case of multiple hormone deficiencies, corticosteroid replacement has to precede thyroid hormone replacement therapy by several days in order to avoid adrenal crisis.

In case of prolonged steroid therapy or treatment with immunosuppressives consider the possibility of opportunistic infections and tuberculosis reactivation. Careful monitoring and consideration of administration of prophylactic antibiotics where appropriate are warranted.

Commonly, referral to experts in the management of organ-specific conditions is highly recommended, especially for irAEs grade 3 or grade 4, or irAEs where management is complex.

BI 754091 and BI 891065 should be permanently discontinued for immune related

- encephalitis, aseptic meningitis, transverse myelitis, or Guillain-Barre syndrome of any grade
- acquired thrombotic thrombocytopenic purpura of any grade
- myocarditis of any grade
- myasthenia gravis, peripheral neuropathy or autonomic neuropathy of grade ≥ 3
- myositis grade 2 with objective findings (see below), any myositis grade ≥ 3
- hepatitis grade ≥ 3 (transaminase >5 times ULN or total bilirubin >3 times ULN), recurrent hepatitis grade ≥ 2
- nephritis grade ≥ 3 , persisting grade 2 nephritis unresponsive to initial steroid therapy or worsening, and recurrent nephritis grade ≥ 2
- pneumonitis grade ≥ 3
- rash, bullous dermatoses, severe cutaneous adverse reaction, Stevens Johnson Syndrome, toxic epidermal necrolysis of grade 4, and recurrent rash grade ≥ 3
- colitis grade 4, and recurrent colitis of any grade
- uveitis, iritis, episcleritis of grade ≥ 3
- autoimmune-hemolytic anemia grade ≥ 2
- haemolytic uremic syndrome grade ≥ 3
- immune thrombocytopenia grade 4

- any recurrent irAE grade ≥ 3 ,
- inability to taper steroids to 10 mg or less prednisone or equivalent within 12 weeks, or
- persistent Grade 2-3 AEs that do not recover to Grade 1 or less within 12 weeks.

Dose adjustment of BI 754091 and BI 891065 besides interrupting or permanently discontinuing BI 754091 and BI 891065 are not allowed.

In rare situations when benefit and risk assessment is considered positive for a patient to continue BI 754091 and BI 891065 treatment despite guidance to permanently discontinue (e.g. in case no alternative anti-cancer therapy is available), it should be discussed with the sponsor.

Pneumonitis:

- For Grade 1 pneumonitis with radiographic evidence of worsening, withhold BI 754091 and BI 891065 until improvement or resolution; BI 754091 and BI 891065 may be reintroduced upon radiographic improvement. In the absence of radiographic improvement within 3-4 weeks, follow guidance as for grade 2 event.
- For Grade 2 pneumonitis, hold BI 754091 and BI 891065 until resolution to at least grade 1. If not already started, initiate therapy for the event as per available guidelines. Follow guidance as for grade 3 pneumonitis if no clinical improvement after 48 -72 hr of starting therapy.
- For Grade 3-4 pneumonitis, permanently discontinue BI 754091 and BI 891065 and immediately initiate treatment according to available guidelines.

Diarrhoea/Colitis:

- For Grade 1 diarrhoea/colitis, consider interruption of BI 754091 and BI 891065 therapy.
- For Grade 2 diarrhea/colitis, withhold BI 754091 and BI 891065 until patient's symptoms recovered to grade 1 or less. Consider initiating treatment with steroids.
- For Grade 3 diarrhoea/colitis, withhold BI 754091 and BI 891065 and immediately start treatment (steroids, non-steroidal immunosuppressents) as per available guidelines.
- For Grade 4 diarrhoea/colitis, permanently discontinue BI 754091 and BI 891065 and immediately commence adequate therapy (e.g. i.v. corticosteroids).
- For Grade 1-3 colitis, restart of BI 754091 and BI 891065 may be considered once symptoms improve to Grade 1 or less without need for continued steroids. After careful benefit risk assessment, BI 754091 and BI 891065 may also be restarted after recovery to grade 1 or less, and on corticosteroid ≤ 10 mg per day
- BI 754091 and BI 891065 should be permanently discontinued for recurrent diarrhoea/colitis of any grade.

Diabetes

- Consider withholding BI 754091 and BI 891065 in case of grade 2 hyperglycemia. Check for ketonuria. In case of new onset of diabetes or unexpected worsening of pre-existing diabetes, check for new manifestation of type 1 diabetes.
- For new onset Type 1 diabetes mellitus, or Grade 3-4 hyperglycaemia associated with ketosis (ketonuria or metabolic acidosis)
 - Initiate insulin therapy
 - Evaluate subjects as appropriate per available guidelines regarding presence of type 1 diabetes
 - BI 754091 and BI 891065 should be withheld until glucose level is controlled with insulin with no sign of ketoacidosis.
- BI 754091 and BI 891065 may be restarted once insulin therapy has established stable glycemic control

Thyroid disorders:

For diagnosed thyroid disorders, thyroid hormone supplementation and monitoring should occur as per available guidelines

- Primary hypothyroidism:
 - For Grade 1 hypothyroidism, BI 754091 and BI 891065 may be continued, with regular monitoring of thyroid values.
 - For Grade 2 hypothyroidism, consider withholding BI 754091 and BI 891065
 - For Grade 3-4 hypothyroidism, withhold BI 754091 and BI 891065, consider admission and IV therapy, especially in case of myxedema
 - BI 754091 and BI 891065 may be restarted once symptoms resolve to baseline with appropriate thyroid hormone supplementation
- Primary hyperthyroidism
 - For Grade 1 hyperthyroidism, BI 754091 and BI 891065 may be continued , with regular monitoring of thyroid values.
 - For Grade 2 hyperthyroidism, consider withholding BI 754091 and BI 891065, initiate therapy as per available guidelines.

- For Grade 3-4 hyperthyroidism, withhold BI 754091 and BI 891065. Consider hospitalization, especially in case of thyrotoxicosis.
- BI 754091 and BI 891065 may be restarted once symptoms resolve to baseline.

Note: in case of concomitant adrenal dysfunction, this must be corrected first, prior to thyroid hormone replacement (reduced stress tolerance)

Adrenal insufficiency

- Interruption of BI 754091 and BI 891065 therapy should be considered for adrenal insufficiency grade 1 or 2, and is warranted for grade 3 and grade 4 adrenal insufficiency, until patient is stabilized on hormone replacement therapy.
- Therapy with BI 754091 and BI 891065 may be restarted once stable replacement therapy has been achieved.
- Note: in case of concomitant hypothyroidism, steroid replacement therapy should precede thyroid hormone substitution to avoid adrenal crisis.

Hypophysitis:

- Diagnostic workup for hypophysitis should be considered e.g. for patients with multiple endocrinopathies, unexplained fatigue, new severe headaches or vision changes.
- Patients should be appropriately advised regarding potentially reduced stress tolerance and increased substitution demands e.g. in case of infections, and to wear a medical alert bracelet to inform medical personnel about potentially increased hormone demands in situations of stress, in case of emergencies.
- Interruption of BI 754091 and BI 891065 therapy should be considered for Grade 1 or 2 hypophysitis, and is warranted for Grade 3 and higher hypophysitis, until patient is stabilized on hormone replacement therapy.

Hepatitis:

- Work-up for other causes of elevated liver enzymes, see also section on potential DILI.
- For Grade 1 hepatitis (elevated AST/ALT < 3x ULN and/or total bilirubin <1.5x ULN), BI 754091 and BI 891065 may be continued, close monitoring of liver values is warranted.
- For Grade 2 hepatitis (AST/ALT 3–5x ULN and/or total bilirubin >1.5 to ≤ 3x ULN), BI 754091 and BI 891065 should be suspended. Monitoring of liver values every 3 days is recommended. Initiate treatment according to available guidelines. Restarting of BI 754091 and BI 891065 may be considered upon recovery to grade 1 or less, and on corticosteroid ≤ 10 mg per day.
- For Grade 3 or higher hepatitis, BI 754091 and BI 891065 has to be permanently discontinued.

Nephritis:

- For Grade 1 nephritis, consider temporarily withholding BI 754091 and BI 891065.
- For Grade 2 nephritis, withhold BI 754091 and BI 891065. Consult nephrology. Initiate treatment according to guidelines. In case of no improvement or worsening, permanently discontinue BI 754091 and BI 891065. BI 754091 and BI 891065 may only be re-started upon recovery to grade 1 or less, and on corticosteroid ≤ 10 mg per day.

- For Grade 3 or higher nephritis, permanently discontinue BI 754091 and BI 891065. Consult nephrology. Treat with steroids 1-2 mg/kg prednisone or equivalent. If improved to grade 1 or less, taper corticosteroids over no less than 4-6 weeks.
- BI 754091 and BI 891065 should also be permanently discontinued for recurrent nephritis grade 2 or higher.

Rash

- For Grade 1 rash, continue BI 754091 and BI 891065. Initiate topical treatment.
- For Grade 2 rash, BI 754091 and BI 891065 may be continued, in case of no improvement upon weekly monitoring, consider interruption of BI 754091 and BI 891065 therapy. Treat topically, add systemic corticosteroid therapies as clinically appropriate.
- For Grade 3 rash, withhold BI 754091 and BI 891065. Initiate topical and systemic therapy as per available guidelines. Upon improvement of event to grade 1 or less, and on corticosteroid ≤ 10 mg per day, consult with dermatology whether therapy with BI 754091 and BI 891065 might be restarted, especially in case no alternative anti-neoplastic therapy is available.
- For Grade 4 rash, BI 754091 and BI 891065 should be permanently discontinued.
- BI 754091 and BI 891065 should also be discontinued for recurrent rash grade 3 or higher.

Bullous dermatosis

- For Grade 1 bullous dermatosis, use local wound care and observation. BI 754091 and BI 891065 can be continued.
- For Grade 2 bullous dermatosis, withhold BI 754091 and BI 891065. Administer topical therapy, add systemic therapy as clinically adequate.
- For Grade 3 bullous dermatosis, withhold BI 754091 and BI 891065, initiate topical and systemic therapy as per available guidelines. Restarting of BI 754091 and BI 891065 may be considered after dermatology consultation.
- For Grade 4 bullous dermatosis, permanently discontinue BI 754091 and BI 891065.

Severe cutaneous adverse reaction (SCAR), Stevens Johnson Syndrome (SJS), Toxic Epidermal Necrolysis (TEN)

- For Grade 2 events, withhold BI 754091 and BI 891065, initiate treatment as per available guidelines. Closely monitor for improvement or worsening.
- For Grade 3 events, withhold BI 754091 and BI 891065. Initiate treatment as per available guidelines. In case mucous membranes are affected, involve appropriate disciplines in management to prevent sequelae from scarring (e.g. ophthalmology).
- For Grade 4 events, permanently discontinue BI 754091 and BI 891065, immediately administer adequate therapy. Immediate admission to burn center or intensive care with dermatology and wound care is recommended, involve appropriate other disciplines as needed in management of mucosal involvement.

In case of Grade 2 or Grade 3 events, BI 754091 and BI 891065 may only be re-started upon event recovered to Grade 1 or less, on corticosteroid ≤ 10 mg per day, and after consultation with dermatology.

Encephalitis/Aseptic meningitis

- BI 754091 and BI 891065 should be permanently discontinued for any grade.

Myasthenia gravis

- For Grade 2 myasthenia gravis, withhold BI 754091 and BI 891065,
- For Grade 3 or 4 myasthenia gravis, permanently discontinue BI 754091 and BI 891065

Guillain Barré Syndrome (GBS)

- Discontinue BI 754091 and BI 891065 permanently for any grade GBS.

Transverse Myelitis

- Discontinue BI 754091 and BI 891065 permanently for any grade transverse myelitis.

Peripheral neuropathy, autonomic neuropathy

- For Grade 1 events, may continue BI 754091 and BI 891065, but with low threshold to discontinue while monitoring closely for worsening.
- For Grade 2 events, withhold BI 754091 and BI 891065 until resolution to grade 1 or less, and on corticosteroid ≤ 10 mg per day. Initiate therapy as appropriate per available guidelines.
- For Grade 3 or grade 4 events, permanently discontinue BI 754091 and BI 891065.

Inflammatory Arthritis

- For Grade 1 arthritis, BI 754091 and BI 891065 can be continued. Administer analgetic treatment (acetaminophen, NSAID).
- For Grade 2-4 arthritis, withhold BI 754091 and BI 891065. Initiate treatment as per available guidelines, cave regarding reactivation of tuberculosis/opportunistic infections in case of prolonged immunosuppressive/DMARD therapy.

BI 754091 and BI 891065 may be restarted after consultancy with rheumatology once recovery to grade 1 or less, and on corticosteroid ≤ 10 mg per day.

Myositis

Diagnostic workup should consider the need to also evaluate myocardial involvement.

- For Grade 1 myositis, BI 754091 and BI 891065 may be continued. Initiate adequate therapy as clinically warranted. In case of elevated CK or muscle weakness, treat as grade 2.
- For Grade 2 myositis, withhold BI 754091 and BI 891065, discontinue permanently in patients with objective findings (elevated enzymes, abnormal EMG, abnormal muscle MRI or biopsy). Initiate therapy as per available guidelines. Resuming BI 754091 and BI 891065 may be considered in patients without objective findings, symptoms have resolved to grade 1 or less without any immunosuppressive therapy, and after consultation with rheumatology/neurology.
- For Grade 3 or 4 myositis, permanently discontinue BI 754091 and BI 891065.
- BI 754091 and BI 891065 should be permanently discontinued if there is any evidence of myocardial involvement.

Polymyalgia-like syndrome

- For Grade 1 event, BI 754091 and BI 891065 can be continued.

- For Grade 2 event, withhold BI 754091 and BI 891065 and promptly initiate adequate therapy. If no improvement, treat as grade 3.
- For Grade 3 or G4 event, withhold BI 754091 and BI 891065, promptly initiate adequate therapy Rheumatology consultancy is highly recommended.

BI 754091 and BI 891065 may be resumed after careful assessment of risks and benefits, rheumatology consultancy highly recommended prior to reinitiation. BI 754091 and BI 891065 may only be re-started upon recovery to grade 1 or less and on corticosteroid ≤ 10 mg per day.

Myocarditis

- Discontinue BI 754091 and BI 891065 permanently for any grade of myocarditis.

Uveitis/Iritis, Episcleritis

- For Grade 1 events, treatment with BI 754091 and BI 891065 can continue. Treat topically as needed.
- For Grade 2 events, withhold therapy with BI 754091 and BI 891065, urgent ophthalmology referral is recommended. Initiate topical treatment, consider systemic therapy if needed. Restart of BI 754091 and BI 891065 is permitted once resolved to grade 1 or less, and off systemic steroids (for the ocular condition, if steroids needed for other irAEs, up to 10 mg prednisone or equivalent are permitted). Continuation of topical/ocular steroids is permitted and does not prohibit resuming BI 754091 and BI 891065 therapy.
- For Grade 3 or 4 events, permanently discontinue BI 754091 and BI 891065 therapy. Seek emergent ophthalmology consultation.. Initiate adequate local and systemic treatment.

Autoimmune-hemolytic anemia (AIHA)

- For Grade 1 AIHA, continue treatment with BI 754091 and BI 891065. Close follow-up of anemia and other lab values.
- For Grade 2-4 AIHA, discontinue BI 754091 and BI 891065 permanently. Initiate systemic therapy as per guideline. Consult Hematology.

Acquired thrombotic thrombocytopenic purpura (TTP), haemolytic uremic syndrome.

Timely recognition upon suggestive findings is essential, timely/immediate involvement of hematology consultancy may be beneficial.

- For any grade TTP, permanently discontinue BI 754091 and BI 891065.
- For HUS (TTP excluded), withhold BI 754091 and BI 891065 for grade 1 and grade 2, provide supportive care. Upon full recovery, BI 754091 and BI 891065 may be restarted after carefully weighing of risks and benefits.
- For Grade 3 or Grade 4 HUS, discontinue BI 754091 and BI 891065 permanently.

Immune thrombocytopenia (ITP)

- In case of Grade 1 ITP, BI 754091 and BI 891065 can be continued.
- For Grade 2 or Grade 3 ITP, withhold BI 754091 and BI 891065 and initiate systemic therapy. BI 754091 and BI 891065 may be restarted upon resolution to at least grade 1.
- For Grade 4 ITP, permanently discontinue BI 754091 and BI 891065.

